7.5.2.2 Time-to-event endpoints

[figure not shown]
Separate Kaplan-Meier plots will be presented by randomised treatment group and overall (total group) for time-to-event endpoints defined in [Section 5.2.2](#). Kaplan Meier estimates and confidence intervals (using Greenwood variance formula) for the cumulated time-to-event rate will be calculated at 24 weeks and at 52 weeks. Q1, median and Q3 of the time to event will be presented, if reached. No statistical test will be performed.

[figure not shown]
7.5.2.3 Categorical endpoints, safety and tolerability endpoints

Only descriptive analyses in the form of frequency tables will be performed.

7.8 SAFETY ANALYSIS

7.8.1 Adverse Events

Adverse events will be coded using the current Medical Dictionary for Regulatory Activities (MedDRA) version in use at BI at the time of database lock. The analyses of AEs will be descriptive in nature.

All analyses of AEs will be based on the number of patients with AEs and NOT on the number of AEs. To account for the variable length of exposure to treatment in both study periods tables will be presented including count and percentage of patients with AE and the incidence rates of AEs with time at risk and rate per 100 patient years. Please refer to [Section 7.8.1.1](#) for further details on the derivation of time at risk and exposure-adjusted incidence rates.

Since this study consists of a double-blind, placebo-controlled part and an open-label part with nintedanib treatment only, three treatment periods will be used for analysis and definition of “treatment-emergent”:

- 1. Double-blind period:** Analyses of AEs will be presented by treatment group and overall. Only adverse events with onset or worsening on or after date of treatment start until end of double-blind period (defined as the day before first intake of open-label nintedanib or last double-blind drug intake + residual effect period, whichever is earlier) will be considered as treatment-emergent and will be included in the analysis. Adverse events will be counted under the treatment as randomized for the double-blind period.
- 2. Nintedanib exposure period:** Analyses of AEs will be presented by randomized treatment group and overall. All adverse events with onset or worsening on or after first intake of nintedanib (double-blind or open-label period) until last intake of nintedanib (double-blind or open-label period) + residual effect period will be considered as treatment-emergent and will be included in the analysis.

3. Over the whole-trial: Analyses of AEs will be presented by treatment group and overall. All adverse events with onset or worsening on or after date of treatment start until last drug intake + residual effect period will be considered as treatment-emergent and will be included in the analysis. Adverse events will be counted under the treatment as randomized for the double-blind period.

In case an AE starts on first day of open-label treatment, it is assigned to the open-label period (and not to the double-blind period).

For further details on summarization of AE data, please refer to ([8](#), [17](#)).

All AEs occurring before first trial drug intake will be assigned to ‘Screening period’ and all AEs occurring after the residual effect period will be assigned to ‘Follow-up period’ or ‘Post-study period’ (for listings only). All adverse events occurring between the start and the end of an interruption of the trial drug will be assigned to ‘off-treatment’ period in the listings. For details on the treatment definition, see [Section 6.1](#).

According to ICH E3 ([18](#)), in addition to deaths and serious adverse events, ‘other significant’ AEs need to be listed in the clinical trial report. These will be any non-serious adverse event that led to an action taken with study drug (e.g. discontinuation or dose reduced).

Summary tables will be produced for non-serious adverse events meeting part (i) of the definition. Part (ii) of the definition will be covered by the analysis of laboratory data. Please refer to [Section 7.8.2](#) for further information.

Adverse events related to gastrointestinal perforation, bleeding and hepatic injury, pathological findings identified on bone imaging and stunted growth identified on dental imaging are considered as protocol-specified AEs of special interest (AESIs), and are ticked as such in the eCRF.

Analysis of AEs in double-blind period:

An overall summary of AEs will be presented by treatment group and overall for the double-blind period of the study.

The following tables will also present number and percentages of patients with respective AEs and in addition the incidence rates of AEs with time at risk and rate per 100 patient years by treatment and overall. Please refer to [Section 7.8.1.1](#) for further details on the derivation of time at risk and exposure-adjusted incidence rates.

The frequency of patients with adverse events, will be summarized by primary system organ class (SOC) and preferred term (PT). The system organ classes (SOC) will be sorted according to the standard sort order specified by EMA, preferred terms will be sorted by decreasing frequency in the total column (within SOC).

Separate tables will also be provided for patients with

- serious AEs (SAEs)
- severe AEs
- other significant AEs (as defined by point (i) of the ICH E3 definition indicated above)
- AEs leading to dose reduction
- AEs leading to permanent treatment discontinuation

- investigator defined drug-related AEs
- AEs leading to death
- protocol-specified AEs of special interest (AESIs) (as ticked on the AE page of the eCRF)
- investigator defined drug-related SAEs
- AEs grouped by safety topic

Adverse event groupings by safety topic have been defined outside the trial protocol, which will be continuously updated at project level (19). These safety topics are deemed of particular importance, and these definitions can be based on selection of coded terms based on MedDRA. The latest approved version of the project level overview archived prior to the respective DBL will be used in the CTR.

The frequency of patients with adverse events within these groupings will be summarized by system, safety topic, subcategory (if applicable) and preferred term. These displays will focus on patients with any adverse event, patients with serious adverse events and patients with investigator defined drug-related adverse events.

Systems will be presented in alphabetical order. Safety topics, subcategories (if applicable) and preferred term will be sorted by decreasing frequency in the total column (within system, safety topic or subcategory).

Analysis of AEs during nintedanib exposure period:

All tables as described for double blind period will be repeated for AEs during nintedanib exposure period for nintedanib treatment only.

Analysis of AEs over the whole-trial:

All tables as described for double blind period will be repeated for AEs in the whole-trial period presenting results by treatment group and overall.

7.8.1.1 Adjudicated adverse events

An independent adjudication committee will review all fatal cases and adjudicate cause of death to respiratory, cardiovascular or other. The adjudication committee will also review all AEs categorized as MACE according to the definition in the adjudication charter.

In addition to standard safety analyses, the frequency of patients with AEs leading to death will be summarized by treatment, adjudicated cause of death (Cardiovascular, Respiratory or Other), and PT.

The frequency of patients with AEs categorized as MACE (that is all AEs categorized as MACE and therefore sent for adjudication) will be summarized by treatment and outcome of adjudication (adjudicated as MACE or adjudicated as not MACE). The frequency of patients with AEs adjudicated as MACE will also be summarized by treatment and PT.

7.8.1.2 Exposure adjusted analysis of adverse events over the whole trial

Time at risk and incidence rates per 100 patient-years will be calculated based on the first onset of an AE in the trial.

Time at risk:

For a specific AE, the total AE time at risk [years] is defined as

$$\frac{\sum \text{Time at risk (days) across all contributing patients}}{365.25}$$

with for each subject the time at risk [days] is defined as follows:

- *Date of first onset of the AE – date of first study drug intake + 1 day* for patients with the specific AE,
- *End of time at risk – date of first study drug intake + 1 day* for patients without the specific AE.

The end of time at risk is defined as the minimum of

- end date of the double-blind, whole-trial and nintedanib exposure treatment period, respectively (incl. REP)
- date of last contact (for definition see [Sec. 5](#))
- date of death
- date of the (interim) database lock.

For the double-blind treatment period, end of time at risk is the day before start of open-label period, in case the patient started open-label treatment before end of double-blind REP.

AE incidence rate:

The AE incidence rate [1/100 patient-years (pt-yrs)] will be calculated as

$$\frac{100 \times (\text{Number of patients with specific AE})}{\text{Total specific AE time at risk [years]}}$$

The 95% confidence intervals for incidence rates are derived using the method described by Rothman and Greenland (2008) ([20](#)).

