6. GENERAL ANALYSIS DEFINITIONS

6.1 TREATMENT(S)

For treatment specifications, please refer to CTP Section 4.

The following trial periods will be defined: screening, post-randomization, blinded treatment period (with sub-periods treatment period, off-treatment, residual effect period and follow-up), open-label treatment period (with sub-periods treatment period, off-treatment, residual effect period and follow-up), nintedanib exposure period (with sub-periods treatment period, off-treatment, residual effect period and follow-up), and post-study as follows (Note: As described below, the last day of each of the following periods is excluded from the respective period. It defines the first day of the subsequent period):

- Screening: from informed consent to randomization
- Post-randomization (optional^[a]): from randomization to first randomized trial drug intake in blinded treatment period
- Double-blind period:
 - Blinded treatment period: from first randomized trial drug intake (or re-start of treatment if interruption) to last blinded trial drug intake (or the day before start date of interruption, if interruption) plus one day
 - Blinded off-treatment (optional^[a]): from start date of interruption to re-start of blinded treatment
 - Residual Effect Period: the Residual Effect Period (REP) of nintedanib for the pediatric program is 28 days. This is the period from the last blinded trial drug intake plus one day to last blinded trial drug intake plus 28 days plus one day or the day of first open-label treatment administration (whichever occurs earlier)
 - Blinded follow-up (optional^[a]): from last blinded trial drug intake plus 29 days up to the beginning of post-study period. This period is only created if last blinded trial drug intake took place more than 28 days before trial completion, or for patients having prematurely discontinued the blinded treatment and still continuing the trial
- Nintedanib exposure period:
 - Nintedanib treatment period: from first nintedanib intake (or re-start of treatment if interruption) to last nintedanib intake (or the day before start date of interruption, if interruption) plus one day
 - Nintedanib off-treatment (optional^[a]): from start date of interruption to re-start of nintedanib treatment
 - Nintedanib residual effect period: from the last nintedanib intake plus one day to last nintedanib intake plus 28 days plus one day

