6.7 BASELINE, TIME WINDOWS AND CALCULATED VISITS

As a general rule, the last assessment/measurement observed prior to start of trial medication will be used as baseline. If the time of the assessment/measurement was not captured, and it was on the same day trial medication started, it will be assumed that it was taken prior to the intake of trial medication. For the nintedanib-exposure period, the last measurement prior to the first nintedanib intake was defined as the baseline measurement.

Visit windowing will be performed as described in the following tables, in order to assign data to the relevant study visit based on the actual day of the assessment. Data will be analyzed using the re-calculated visits in the statistical tables. However, in the listings, all visits performed will be displayed (even if outside time-window), along with the re-calculated visit.

Exception:

to account for the short timespan between planned visit 6 (with first open-label intake) and visit 7, a special rule is applied to analyses by visit (not cumulative across visits) in case assignment to visit windows leads to missing values at visit 6 or subsequent visit to take possible multiple measurements in the respective other time window into account.

If such an assessment lies in analysis visit window of visit 7, but not later than 1 month after the planned day of visit 7 and still within the double-blind period, then it is allocated to the analysis visit 6.

Similarly, if such an assessment lies in analysis visit window of visit 6, but after the planned day of visit 6 and not within the double-blind period, then it is allocated to the subsequent visit where this assessment is planned.

If after windowing of visits at baseline, two or more values fall within the same baseline interval, then the last value prior to first drug intake will be taken into account. If after windowing of post-baseline visits, two visits fall in the same interval, then the measurement closest to the planned visit will be taken into account. If only on-treatment values are to be considered, this rule will be applied to on-treatment assessments only. In case two measurements are equidistant from the planned visit, then the last one will be picked.

Table 6.7: 1 Time windowing rules for FVC, SpO₂, missed school days, vital signs (syst. and diast. blood pressure, pulse rate) and laboratory tests (incl. LDH)

Time window of actual day ^[1,2]			Allocated to		

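### As written, SAP 7.8.1.2 starts risk time at the first study-drug dose in every period, so the nintedanib-period adverse event rates carry about 24 weeks of placebo time per switched patient

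*SAP*

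**What the plan says.** SAP 7.8.1 analyses AEs over three periods: double-blind, nintedanib exposure and whole trial. For the nintedanib exposure period the events counted are "All adverse events with onset or worsening on or after first intake of nintedanib (double-blind or open-label period) until last intake of nintedanib" plus the residual effect period (REP), shown by randomised group and overall. The double-blind tables include time at risk and rate per 100 patient-years, and "All tables as described for double blind period will be repeated for AEs during nintedanib exposure period for nintedanib treatment only".

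Section 7.8.1 sends the reader to 7.8.1.1 "for further details on the derivation of time at risk and exposure-adjusted incidence rates". Section 7.8.1.1 covers adjudicated events and contains no derivation. The formula is in 7.8.1.2:

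- **Event:** "Time at risk and incidence rates per 100 patient-years will be calculated based on the first onset of an AE in the trial".
- **Start:** both the formula for patients with the event and the one for patients without it close with "date of first study drug intake + 1 day", with no period qualifier.
- **End:** the earliest of several dates, one being the "end date of the double-blind, whole-trial and nintedanib exposure treatment period, respectively (incl. REP").

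Two other sections anchor this period at nintedanib. SAP 6.1 has "Nintedanib treatment period: from first nintedanib intake", and SAP 6.7 has "For the nintedanib-exposure period, the last measurement prior to the first nintedanib intake was defined as the baseline measurement".

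**The concern.** The end of risk changes with the period, but the start does not. SAP 6.1 runs the whole-trial period from the first randomised dose to the last study-drug dose, so study drug there includes placebo. A patient randomised to placebo therefore enters the nintedanib denominator about 24 weeks before any event can be counted.

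A second phrase works in the opposite direction. If first onset is taken over the whole trial, an event on placebo can end risk time before nintedanib starts, although the patient may be counted again for the same event on nintedanib.

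Section 7.8.1 says the rates are there to allow for unequal exposure. As written, they add placebo time to one randomised column and to the overall column but not to the other, so the columns are not on the same footing. These tables feed the safety picture at the first database lock (DBL 1), whose benefit-risk assessment decides whether the extension trial starts (Protocol 3.1).

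**Working it through.** The documents give no AE rate or patient-years, so there is no planned figure to reproduce. I applied the SAP formula, rate = 100 × patients with the event ÷ years at risk, with each start date in turn.

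**Inputs**
- About 20 patients on nintedanib and 10 on placebo (Protocol synopsis); Part A lasts 24 weeks (Protocol 3.1).
- Recruitment over 18 months, at least 26 weeks of treatment, mean nintedanib exposure of about 12 months (Protocol 3.2).
- Assumed: all 10 placebo patients switch at week 24 and stay on treatment to the data cut; REP time ignored.

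**One patient.** An event 14 days after the first nintedanib dose contributes 14 + 1 = 15 days from nintedanib start, but 168 + 15 = 183 days as written.

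**Placebo time added.** 10 × 24 = 240 weeks; 10 × 168 ÷ 365.25 = 4.6 patient-years.

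**Rare event** (truncation at onset negligible). Let F be mean follow-up from randomisation in weeks. Matched time is 20F + 10(F − 24); time as written is 30F. Two values of F come from the protocol:
- Uniform 18-month (78-week) recruitment gives follow-up of 26 to 104 weeks, so F = 65.
- Mean nintedanib exposure is (20F + 10(F − 24)) ÷ 30 = F − 8. Setting this to 52 weeks gives F = 60.

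The longer values, 78 and 104 weeks, are assumed.

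| F | Matched weeks | As written | Overall ratio | Placebo-randomised column, (F − 24)/F |
|---|---|---|---|---|
| 60 | 1560 | 1800 | 0.867 | 0.600 |
| 65 | 1710 | 1950 | 0.877 | 0.631 |
| 78 | 2100 | 2340 | 0.897 | 0.692 |
| 104 | 2880 | 3120 | 0.923 | 0.769 |

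The overall rate is thus 12% to 13% too low at F = 60 to 65, 10% at 78 and 8% at 104. The placebo-randomised column is 37% to 40%, 31% and 23% too low.

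**Common early event** (assumed: 60% of patients, at nintedanib week 4, none earlier on placebo; F = 65). Mean weeks at risk per patient:
- Placebo-randomised, matched: 0.6 × 4 + 0.4 × 41 = 18.8.
- Placebo-randomised, as written: 0.6 × 28 + 0.4 × 65 = 42.8.
- Nintedanib-randomised, either way: 0.6 × 4 + 0.4 × 65 = 28.4.

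With 365.25 ÷ 7 = 52.18 weeks per year, the placebo-randomised rate is 60 × 52.18 ÷ 18.8 = 167 per 100 patient-years matched and 60 × 52.18 ÷ 42.8 = 73 as written. The ratio is 0.44, or 56% too low. Overall: (20 × 28.4 + 10 × 18.8) ÷ (20 × 28.4 + 10 × 42.8) = 756 ÷ 996 = 0.76, or 24% too low.

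**Earlier onset on placebo.** Suppose a share p of switched patients already had the event at placebo week 4. If risk time is cut for all of them, mean weeks as written are 4p + 42.8(1 − p). If it is cut only for those also counted on nintedanib, they are 28.4p + 42.8(1 − p), where 28.4 = 0.6 × 4 + 0.4 × 65.
- p = 0.25: 33.1 or 39.2 weeks; ratio 18.8/33.1 = 0.57 or 18.8/39.2 = 0.48.
- p = 0.50: 23.4 or 35.6 weeks; ratio 0.80 or 0.53.
- On the first reading the two errors cancel at p = (42.8 − 18.8) ÷ (42.8 − 4) = 0.62. Above that the rate is too high.

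**The case against.** The strongest reply is that this is a drafting slip. The heading of 7.8.1.2 refers to the whole trial, for which the formula is right, and it is also right for the double-blind period. SAP 5.4.3 calculates exposure from the first administration in each period, and 6.1 and 6.7 anchor the nintedanib period at first nintedanib intake. Section 7.8.1 defines treatment-emergent events period by period, so a placebo-phase onset may never reach the nintedanib-period data. The analysis dataset plan and sponsor standards, which are not available here, may settle the programming. I agree that a period-specific start was probably intended. But 7.8.1.2 is an explicit formula that names this period, and a programmer following it gets the wrong denominator.

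The reply is also right that the event frequencies and earlier-onset shares are assumed, that some patients may have a shorter Part A (Protocol 3.1, 7.5), and that placebo patients who never switch do not enter this period. The analyses are descriptive, no test between columns is planned, and a column of about 10 patients is imprecise in any case. Time at risk is printed beside the rate, so an alert reader might notice the surplus. These points limit the consequence but do not remove the mismatch.

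The related places are unclear rather than wrong. In 5.4.4.1 the start of treatment has no period qualifier, although 5.4.4 says the analysis is done by period. Section 7.8.1.3 borrows the censoring rules without stating a time origin for its nintedanib-period Kaplan-Meier plots.

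**Conclusion.** The concern holds. Applied as written to the nintedanib exposure period, 7.8.1.2 pairs events counted from first nintedanib intake with risk time counted from the first placebo dose in switched patients. The rare-event figures (overall 12% to 13% too low, placebo-randomised column 37% to 40% too low) rest on 30 patients randomised 2:1, all placebo patients switching at week 24, and mean follow-up of 60 to 65 weeks. The larger common-event figures also depend on assumed incidence and timing. The first-onset wording can offset or reverse the error when the same event is frequent on placebo.

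The start date does not affect the nintedanib-randomised column, patients entered directly into Part B, double-blind and whole-trial rates, any N (%) figure or the primary endpoints. The point should be fixed, but it does not threaten the trial's main conclusions.

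**What to change.** In SAP 7.8.1.2, define the start as the first study-drug dose in the period being analysed, which for the nintedanib exposure period is the first nintedanib dose, and define the event as first onset within that same period. Make both changes together. Moving only the start would give negative risk time for a patient whose first onset was on placebo: onset at week 4 minus nintedanib start at week 24 is −20 weeks.

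For consistency, add the period qualifier to the start date in 5.4.4.1, state the time origin for the plots in 7.8.1.3, and point the cross-references in 7.8.1 to 7.8.1.2.

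The cost is a few words in the SAP and one period-specific start date in the analysis datasets. No new data are needed.

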7.8.1.3 Adverse events with additional information collection

Diarrhea, bleeding and ILD are AEs with additional AE-specific information collected on the eCRF. These are investigator reported on the eCRF and will be identified using this information for this analysis. That is if the diarrhea information has been completed for an adverse event then the adverse event will be considered as diarrhea for this analysis regardless of subsequent MedDRA coding of the verbatim term. Likewise, if the bleeding information has been completed for an adverse event then the adverse event will be considered as bleeding for this analysis regardless of subsequent MedDRA coding of the verbatim term. The same applies to ILD.

The frequency of patients with AEs with additional information collection will be summarized by treatment group and overall, primary SOC and PT and separately for diarrhea, bleeding and ILD. The additional information collected will also be summarized at the AE level (occurrence level) rather than at the patient level separately for diarrhea, bleeding and ILD. These analyses will be provided by analysis periods and treatment group and overall, where applicable.

For the time to first onset of diarrhea, bleeding or ILD, respectively, Kaplan-Meier plots by treatment will be created taking into account the respective data over the whole trial. Kaplan-Meier plots of the double-blind period and the nintedanib exposure period will be created as well. The same censoring rules as for time to first liver enzyme elevation trial will be used, see [Section 5.4.4.1](#) for details.

7.8.1.4 Pathological findings of epiphyseal growth plate on imaging, on dental examination or dental imaging

Adverse events identified based on imaging or dental examination will be reported in the Adverse Event page of the eCRF and will be listed in the standard AE tables and listings.

